The maintenance exercise group is a commissioned exercise group post pulmonary rehabilitation. Patients are invited to join a class to ensure they continue to exercise at a prescribed level. This group also provides valued social contact. Continued exercise is vital to ensure physical wellbeing but might be continued outside a clinical setting in a way, which also enhances social contact to replace the social role that the maintenance exercise group currently holds for COPD patients. The current clinical contact time could be replaced by voluntary groups and other exercise providers including informal contacts linked into personal networks of support which might ensure an equivalent or enhanced supportive social environment which is less reliant on existing health care services.

The supportive self-management tool GENIE (Generating Engagement in Network Involvement) has been implemented effectively in a 'My LIFE a Full life' (MLAFL), project, based on the Isle of Wight, (Kennedy et al 2016). The MLAFL programme focuses on people with long-term conditions, older people and those with mental health needs, with three priority areas identified:

- Self-Care and Self-Management
- Crisis Response
- Locality Working

The GENIE implementation purposefully sampled people with type 2 diabetes in order to represent the long-term conditions group. Diabetes is a long term life limiting condition, with episodes of acute illness- during hypo/hyper-glycemic events. However COPD is different to diabetes because of limitations caused by breathlessness which can be physically disabling and socially isolating. Therefore implementing and evaluating this already successful social mapping tool into the COPD service is valuable to understand:

- Differences and similarities in its utility for different Long term conditions
- Barriers to social activity including those linked to a person's physical condition
- Response, uptake and practical benefits of GENIE for COPD patients
- Capacity of voluntary, community and personal network to take on the work previously undertaken in the maintenance clinic.
- Health economic and service utilisation benefits
- Exploration of weak or fractured social networks in COPD

Purpose

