The main aim here is to increase long term health care management options in Solent NHS Trust by building social capacity to support self-management. The GENIE tool will be introduced into the COPD service to improve options for social groups and exercise when leaving a pulmonary rehabilitation group, or when clinically unable to participate in exercise.

- to build social networking awareness and the importance of utilising existing social resources in the professional and voluntary members of the COPD service,
- to use social network mapping techniques and preference elicitation to engage COPD patients in reflecting on their support preferences and needs, help them access further resources and knowledge
- Evaluate the success of the social mapping techniques (GENIE) in the COPD patient population
- Evaluate the cost benefit to both to patients and to the health service of the GENIE in the COPD patient population

Objectives

Primary objectives

Compare and evaluate the health care utilisation and quality of life (burden of disease) in COPD patients using GENIE alongside usual care after leaving the COPD service with those offered only a current practice discharge plan.

Secondary objectives

Compare and evaluate the change in health behaviours, in particular diet and lifestyle in COPD patients using GENIE alongside usual care after leaving the COPD service with those offered only a current practice discharge plan.

Observe and understand the uptake and utilisation of the GENIE recommendations by COPD patients.

Explore social complexities in the COPD population.

Implementation Design

[figure not shown]
This protocol is concerned with the implementation and evaluation of the GENIE tool in the community facilitated by the COPD team and the subsequent evaluation of the GENIE in direct comparison to usual clinical practice.

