Block randomisation technique, a commonly used technique in clinical trial design to reduce bias and achieve balance in the allocation of participants to treatment arms, especially in this case when the sample size is small (Efird, J. 2010). In order to reduce unconscious bias of the researcher, pre-prepared envelopes containing the possible combinations of group allocation, will be stored in a locked drawer in Bitterne Health Centre. The intention is to randomize in blocks of four, as this will complement the clinic structure. Therefore, each envelope will contain a pre-determined allocation pattern for that clinic (AABB, ABAB, BABA etc.).

The researcher team will share an excel spread sheet which will be set to generate a random number sequence. The next sequential number will be selected, which will then correspond to an envelope with the predetermined sequence. In this way the envelope selection is random, then sequence in the envelopes is also random, but ensures 50/50 grouping of participants. Baseline data for descriptive statistics will also be collected. (Data capture form appended)

In order to conduct meaningful analysis recruitment needs to reach at least 30 patients, in each group, however the maximum could be 60 in each group, 120 patients in total. Therefore recruitment could take between 6-9 months. The timeframe can be increased if necessary.

Initial / Baseline data collection:

Socio-economic data will be collected including; disease severity (FEV1), gender, EQ-5D, health care utilisation questionnaire, HEIQ and wellbeing questionnaires (CAT, GAD, PHQ-9), as well as an optional health behaviour questionnaire, from both the usual care group and the interventional group. Please note CAT, GAD, PHQ-9 FEV1 and gender are already captured routinely during clinical consultation.

Intervention

[figure not shown]
Assessment stratification and feedback:

Stage 1: The patient will complete a questionnaire online with the researcher/clinician. The patients will be asked to name the important people and activities in their network, type of relationship and frequency of contact using the concentric circles diagram.

Stage 2: The online process: consisting of series of questions will be used to elicit the participant's values and preferences for activities and support resources.

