Stage 3: This section will then link individuals to prioritised and valued activities and resources (links are to a pre-created database where local organisations and resources have been categorised).

Stage 4: The GENIE Tool then presents options in a user-friendly way, on a Google map with clear details about access, an example below:

Both groups will receive usual care, however one arm will have the addition of the intervention both will be called for a review at:

Three monthly follow up (+/- 1 week)

Six questionnaires will be administered. EQ-5D, health utilisation questionnaire, HEIQ and wellbeing questionnaires (CAT, GAD, PHQ-9), as well as the optional health behaviour questionnaire, so in 30 participants this will be seven, these will be repeated at 3 months post intervention (+/- 2 week). Furthermore, for those in the intervention arm, feedback and reflection discussions will be initiated using the network diagrams. Participants will be asked again for their permission to tape record these discussions to ensure parity and quality assurance between researchers.

Analysis of Outcomes

The study gathers data from the intervention arm and the non-intervention arm at baseline and 3 months post intervention. Results will be compared between the groups at baseline and 3 months post intervention. An economic analysis will be performed using a modified version of the Client Service Receipt Inventory (CSRI) (Beecham and Knapp 1999) Medication, health service use will be measured at baseline, 3 months post implementation and follow up. The modified version has been tailored to capture the needs of the target population (COPD patients). The CSRI has been widely used in previous research studies and has been evidenced as a valid measure of frequency of health service use (Patel 2005). The EQ5D is included to assess health status of patients during the GENIE intervention. Wellbeing score (CAT) and HEIQ and in the optional sub-group health behaviours (dietary intake, appetite, alcohol consumption and smoking habits) will be compared at baseline and 3 months. Furthermore, patient uptake of the social activities is to be recorded on paper using the Genie tool and compared between groups.

Rationale for the service implementation and evaluation design

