Participation in the study will be offered to every patient in pulmonary rehabilitation or maintenance exercise programs in the east of Southampton. Participants must also fulfill the inclusion criteria. Patients already referred into pulmonary rehabilitation groups will be approached and asked if they wish to participate in the study at assessment and at the end of pulmonary rehabilitation in their post PR review appointment. The appointments are offered to patients after completion of the patients PR program, usually after 12 sessions by the clinical team. Therefore, it is envisaged that a minimum of 30 patients per arm will be recruited; these include PR leavers, maintenance reviews referrals. Appointments will be offered in person, via the telephone with confirmation letter or text. The numbers from each of these groups cannot be predicted as it is dependent on clinical opinion, however the aim to have a minimum of 30 participants, with the aim to recruit up to 60 to ensure meaningful analysis.

Inclusion criteria;

- adults between 18 and 95 with a predominant diagnosis of COPD
- Ability to understand spoken English
- Enrolled in PR or maintenance therapy
- Ability and capacity to make their own decision and consent freely

Exclusion Criteria;

- No clear COPD diagnosis
- Inability to consent

The Intervention

This evaluation aims to demonstrate the effectiveness and increase social interactions and community networks in the COPD population in Southampton city.

Rational for GENIE is connecting people to new resources

The aim of using GENIE is to connect people with long-term conditions to local and (in the future) online resources to support them in their everyday lives. Objectives of GENIE:

- Raise awareness of the links and functions that social networks enable (for individuals and local community groups and organisations).
- Use social networks to engage patients in reflecting on their needs and support, support access to further resources and knowledge and introduce practices related to lifestyle, illness management, and behaviour change.
- Strengthen existing individual and community networks and improve patient engagement.

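### The promised between-arm comparison of social-activity uptake cannot work as written, and no both-arm measure of exercise or social contact is described, so the trial cannot show by randomised comparison whether GENIE changed either

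*Combined protocol and SAP*

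**What the plan says.** **Intent.** Under Purpose, the tool is brought into the COPD service "to improve options for social groups and exercise when leaving a pulmonary rehabilitation group". Under The Intervention: "This evaluation aims to demonstrate the effectiveness and increase social interactions and community networks in the COPD population in Southampton city". The introduction adds that "Continued exercise is vital to ensure physical wellbeing" and suggests that community provision might take over some of the maintenance class's role.

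**Objectives.** The primary objective is to "Compare and evaluate the health care utilisation and quality of life (burden of disease) in COPD patients using GENIE alongside usual care". Secondary objectives include change in health behaviours, chiefly diet and lifestyle, and to "Observe and understand the uptake and utilisation of the GENIE recommendations by COPD patients".

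**Measurement.** The baseline and three-month sections list EQ-5D, the health care utilisation form, HEIQ, CAT, GAD and PHQ-9 for both arms, with an optional behaviour questionnaire. Analysis of Outcomes says of the optional sub-group that "health behaviours (dietary intake, appetite, alcohol consumption and smoking habits) will be compared at baseline and 3 months". The next sentence says that uptake of social activities is to be noted on paper by means of the GENIE tool and compared across the arms. The Table of Events has an uptake discussion or survey row, marked at 12 weeks and at the possible one-year follow-up, with no arm named.

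**The network map.** Stage 1 of the intervention records network members, "type of relationship and frequency of contact using the concentric circles diagram".

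**The concern.** The plan offers one route to a randomised comparison on the behaviours GENIE is introduced to support, namely social-activity uptake, and that route depends on a tool the control arm does not have. Exercise has no described measure at all.

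This matters for interpretation. If CAT and cost do not differ between arms, the investigators could not tell whether GENIE left behaviour unchanged or changed it without clinical effect. If cost favours GENIE, they could not say whether exercise was kept up. Under Risks / benefits, a favourable result leads to the tool being offered to all patients, so either question could arise in practice.

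The recruits are also mixed. They are people finishing pulmonary rehabilitation and people with a year or more of maintenance classes, in proportions that the Population section says cannot be predicted. Their starting levels of exercise and contact may differ widely, so an uptake record taken only at follow-up is a weak basis for comparing arms.

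**Working it through.** The plan gives no figure on this point to reproduce. The check sets the sections side by side.

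**1. Instruments given to both arms at baseline and 3 months**

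| Instrument | How the documents describe it | Exercise? | Social contact? |
|---|---|---|---|
| EQ-5D | health status | not described | not described |
| Health care utilisation form (appended) | service use, work absence, costs | no; one free-text cost item mentions club or gym membership | no |
| HEIQ | self-management | not described | not described |
| CAT | wellbeing, burden of disease | not described | not described |
| GAD | wellbeing | not described | not described |
| PHQ-9 | wellbeing | not described | not described |
| Behaviour questionnaire (optional) | diet, appetite, alcohol, smoking | not described | not described |

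Only the utilisation form is reproduced in full. For HEIQ and the behaviour questionnaire the supportable statement is that such items are not described, not that they are absent. The gym item records spending, so it is at most a weak proxy for exercise.

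**2. Can the promised uptake comparison be carried out?**

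- *Tool.* Uptake is to be recorded with the GENIE tool. The section on selection and patient information gives that tool to the GENIE group only.
- *Three-month discussion.* The follow-up section limits the feedback discussion based on network diagrams to the intervention arm.
- *Baseline.* The uptake row in the Table of Events has no baseline mark.
- *Analysis.* Items a) to d) of the Analysis Plan cover cost utility, CAT and psychological impact, and uptake is not among them. It appears only under the 12-month survey, as the proportion engaging in recommended activities, with no between-arm test. That follow-up is itself only a possibility.
- *What is counted.* Controls receive suggested activities through discharge planning, while the GENIE arm also receives the tool's suggestions. Engagement in recommended activities would therefore be scored against different lists.
- *Scope.* The record concerns social activities, not the amount of exercise.

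**3. Precision available if the measures are added**

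The documents give 30 to 60 per arm but no alpha, power, SD or dropout. I assume two-sided alpha 0.05, 80% power, 1:1 allocation and no dropout.

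Detectable standardised difference: d = (z₀.₉₇₅ + z₀.₈₀) × √(2/n) = (1.960 + 0.842) × √(2/n).

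- n = 30 per arm: 2.802 × √(2/30) = 0.72
- n = 60 per arm: 2.802 × √(2/60) = 0.51
- Optional sub-group of 30, if split 15 and 15: 2.802 × √(2/15) = 1.02

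Baseline adjustment would reduce these by an amount that depends on a correlation the documents do not give.

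For uptake as a proportion, I solved n = [z₀.₉₇₅√(2p̄(1−p̄)) + z₀.₈₀√(p₁(1−p₁) + p₂(1−p₂))]² / (p₂−p₁)² for p₂, the uptake needed in the GENIE arm, in steps of 0.5 percentage points:

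| Assumed control uptake | 30 per arm | 60 per arm |
|---|---|---|
| 10% | 41% | 30.5% |
| 20% | 54.5% | 44% |
| 30% | 65.5% | 55.5% |
| 40% | 75.5% | 65.5% |

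Only large effects would be detected, and the optional sub-group is too small to carry the question.

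**The case against.** **The stated primary objective is measured.** Utilisation, EQ-5D and CAT are taken in both arms at baseline and 3 months. A reader might infer that the trial cannot show whether GENIE works. The documents do not support that: what is missing is evidence on the intended mechanism. On exercise, Purpose speaks of better options, and no objective commits to a change in amount. This stands, and limits the point to social contact and exercise.

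**A between-arm comparison of uptake is planned.** A reader might infer that no randomised comparison of social behaviour is intended. Analysis of Outcomes says otherwise, and the Table of Events does not confine the uptake row to one arm. The fault is that no workable way of making the comparison is described.

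**The behaviour form serves an objective.** A reader might call diet, alcohol and smoking off target. They fit the secondary objective on diet and lifestyle.

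**Harm.** A reader might infer that a loss of exercise would go unseen. A shift towards sedentary activity is conjecture: both arms keep usual care, and the community options envisaged include exercise providers. Clinically relevant decline could still appear in CAT, EQ-5D or utilisation.

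**The added items are weak.** They would be brief self-reports from participants who know their allocation, in a small trial, and days of contact do not measure a network. This also stands. A null result would not separate no behavioural change from too few patients. The items would still give an estimate with an interval where the plan now gives none.

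**Conclusion.** The point holds in a limited form. The uptake comparison promised in Analysis of Outcomes cannot be made as written: the recording tool belongs to one arm, there is no baseline, and the Analysis Plan contains no three-month uptake analysis. No instrument is described as measuring exercise in either arm, or social contact in both arms at baseline and 3 months. The trial can compare utilisation and quality of life, but as described it cannot show by randomised comparison whether GENIE changed social contact or exercise.

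This rests on how the documents describe the instruments. If HEIQ or the behaviour questionnaire already holds suitable items, the gap narrows to naming them as outcomes and, for the optional form, giving them to everyone. The change should be made before recruitment, because a baseline cannot be recovered later.

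**What to change.** - Add two short items to the core questionnaires and the Table of Events, for all participants in both arms at baseline and 12 weeks: exercise sessions in the last 7 days by setting (COPD-team class, community, home), and days in the last 7 with face-to-face or group contact. If HEIQ or the behaviour questionnaire already contains such items, name those instead and give them to everyone.
- Record activity uptake on the same arm-neutral form in both arms, not through the GENIE tool.
- In the Analysis Plan, name these as secondary outcomes. Compare arms at 12 weeks, adjusting the exercise and contact items for their baseline values, and report estimates with 95% confidence intervals.
- Do not use the network map in controls. Mapping is one of the three elements of GENIE, so it would deliver part of the intervention to them.

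The cost is a short extra form, a protocol amendment and a little more time at each visit, with no new staff or procedures. The items would be self-reported without blinding and imprecise at 30 to 60 per arm, and the plan should say in advance that a null result on them will not be read as evidence of no effect.

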GENIE

Implementing and Evaluating the GENIE tool in Southampton Integrated COPD Service

: A clinical trial and evaluation to ascertain cost effectiveness and patient benefit.

Introduction

Background

COPD is a life limiting progressive illness punctuated by acute episodes; prompting potential solutions through self-management support. Clinical trials in COPD self-management have yielded mixed results (Fan, VS 2012 and Bourbeau, 2003.) However, self-management support and education can reduce health care contacts when delivered and targeted appropriately, (Taylor, 2014).

To date the effectiveness of Self-Management Support (SMS) for COPD based for example on action planning alone has been limited (for example changing utilization patterns) and suggests the need for a more elaborate approach to SMS in clinical settings (Walter J. 2010, Peytremann-Bridevaux 2008 and Taylor 2014).

Decision making processes, as in other conditions may be influenced positively by promoting access to connections and resources through social networks. However to date the concept of socially supportive self-management in COPD has a limited evidence base in terms of how this might be implemented successfully in practice settings.

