The implementation and evaluation of the GENIE tool builds on the early GENIE studies indicating that the intervention will work on the premise that finding out about and enhancing network support can be undertaken by a variety of people (e.g. social network members, members of local community groups, health professionals) in a variety of situations (e.g. at home, work, in public and healthcare settings). Further research is indicating the potential of GENIE in existing health care structures, but has yet not been fully tested. Furthermore, much of the preliminary work was performed in patients with Type II diabetes, understanding how GENIE is received in COPD patients requires further investigation.

Risks / benefits

Each patient leaving pulmonary rehabilitation will be offered usual clinical care; therefore no patient is put at risk. However, it is recognised that the process of divulging and discussing networks and social activity in potentially isolated people, may be potentially distressing. Therefore, the study is still therefore very much grounded within the clinical service. If a person did become distressed, then the interviews and questions would be stopped and the researcher would support the participant in the first instance. The researcher would then be able to refer the participant back into the clinical team, and also request psychological support, through the IAPT / Steps to Wellbeing service, a self-referral psychological service. These participants would also have the option to then withdraw from the study.

The patients in the GENIE intervention arm may have increased benefit due to access and signposting to tailored community resources. Therefore, if a benefit is seen in those participants included in the intervention arm of the study with increased access to services then the GENIE tool will be offered to all patients' post study completion. Ideally, the tool will be implemented and rolled out post study by 'expert users' or participants and or patients who could support others in network support and provision.

Population

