Following the training, the participants will be given the tools required to roll out the intervention

- Paper and web-based concentric circles with typologies and support suggestions
- Guidebook on how to deliver GENIE
- Access to the database and website

Identification, enrolment and randomisation

[figure not shown]

Table of Events

	Consent and Randomisation	Pre – intervention data collection	12 weeks post intervention data collection (+/- 1 week)	Potential 1 year follow up phase
Consent form discussion and taking informed consent	x			
Randomisation (Block)	x			
EQ-5D		X	x	x
Health Care Utilisation Questionnaire		X	x	x
Socio-economic background / demographic data		X		
Gender		X		
Disease severity (FEV1)		X		
HEIQ (Self-management)		X	x	
Optional Health behaviour questionnaire		x	x	x
CAT		X	x	x
Gad-7 /		X	x	
PHQ-9		x	x	x
Uptake discussion / online survey			x	x

Quality Assurance

The delivery of the intervention will be taped in as many cases as consented to ensure that the intervention is delivered consistently by the research team to all patients. The tape recording is for quality assurance, and is not intended for research utilisation or publication.

Future work

The participants included in this initial 3 months of the study could be followed up again in 1 year (12 months) to ascertain longer term outcomes and longevity of connections made. This element could consist of a paper or online survey to understand the uptake rates of the social actives 1 year on, and further investigation into QOL, **healthcare use and the option of assessing health behaviours.** All participants would be given the option of continuing for a year, and therefore those who continue would be decided by participant preference to remain in the study.

Analysis Plan

Primary Outcomes

Descriptive statistics of the cohort,

Descriptive statistics of the cohort will be reported including but not limited to; age, gender, severity of disease then the analysis will be broken down into 5 distinct sections;

- a) Pre and post intervention cost utility analysis for the usual care group and the intervention group.
- b) Comparative group - pre and post cost utility analysis; calculated cost per QALY (quality adjusted life years) gained and cost of healthcare usage per patient– usual care group at 3 months after leaving the COPD service compared with the post intervention group 3 (+/- 1 week) months after leaving the COPD service, with significance.

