- c) Clinical comparative analysis pre and post intervention including burden of disease (CAT score) and psychological impact of the disease, using Wilcoxin Ranked tests. Pre intervention burden of disease correlated with 3 months (+/- 1 week) disease burden post intervention (CAT), with significance.
- d) Clinical comparative analysis between groups at 3 months (as above) Wilcoxin Ranked tests.

12 month follow up survey

- a) Pre intervention burden of disease compared with 12 months disease burden post intervention (CAT).
- b) Activity uptake rates; recorded at 12 months post intervention, proportions of patients engaging in recommended activities.

Ethical Considerations

This is a new research trial of an existing social networking tool already used in long term diseases but not yet specifically in COPD. Prior to introducing this to the entire clinical service, clinical effectiveness recommends changes are trialled on a smaller proportion of the patient population in order to understand the benefits of time and cost prior to full scale implementation.

As this is an intervention within a clinical service and the evaluation is conducted with NHS participants, on NHS properties therefore University ERGO (Ethics) and HRA full NHS ethics application has been sort. The Ethical review number will be on all patient facing documentation. This ethical review has evaluated the social and scientific value of the study. Further to this it ensures adequacy of patient information, the informed consent process, recruitment arrangements and access to information.

The service implementation and evaluation will also be presented at the Solent Adult service line, clinical effectiveness and audit group for Solent NHS Trust approval.

References

Beecham, J. and Knapp, M. **Costing Psychiatric Interventions. Discussion paper.** Chapter for *Measuring Mental Health Needs*. 1999. Ed Thornicroft, G.

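### The only planned 12-month CAT analysis compares participants with their own baseline, so it cannot separate a lasting GENIE effect from disease progression or selective continuation

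*Combined protocol and SAP*

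**What the plan says.** The main study is short. Analysis of Outcomes states: "The study gathers data from the intervention arm and the non-intervention arm at baseline and 3 months post intervention". Item d) of the Analysis Plan compares the groups clinically at 3 months.

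Future work adds a possible later stage: "The participants included in this initial 3 months of the study could be followed up again in 1 year (12 months"). Its stated purpose is to learn about outcomes over the longer term and how durable the new connections are. Every participant may opt to continue, but "those who continue would be decided by participant preference to remain in the study". The Table of Events schedules CAT in its potential 1-year column.

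The Analysis Plan gives the 12-month survey two items. Item a) reads: "Pre intervention burden of disease compared with 12 months disease burden post intervention (CAT"). Item b) is the proportion of patients taking up recommended activities. Neither names a comparison between the randomised arms.

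Risks / benefits contains a conditional promise: "if a benefit is seen in those participants included in the intervention arm of the study", "then the GENIE tool will be offered to all patients", with the offer timed after completion of the study. The documents do not say whether completion means the 3-month visits or the 12-month survey.

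**The concern.** The Background section opens with "COPD is a life limiting progressive illness punctuated by acute episodes". A before-after comparison over a year in such a disease mixes three things: what GENIE did, what the disease did, and who stayed to be measured. A tool that slowed decline could be reported as leaving patients worse than at baseline. A tool with no effect could look helpful if those who deteriorated did not continue. Either result could be read as evidence on durability, which is the purpose of this phase.

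Randomisation provides the means to separate these, because both arms are invited to continue and CAT is scheduled at 1 year. The written plan does not use it at that time point. The open-ended offer of GENIE matters second: it could weaken the arm comparison that would repair the analysis.

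**Working it through.** The plan gives no 12-month sample size, power, retention or expected CAT change, so there is no figure to reproduce.

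**1. What item a) estimates.** Count a rise in CAT as heavier burden. Let p be the mean change from natural progression over 12 months, g the GENIE benefit still present at 12 months, and s1 and s0 the shift in mean change that arises because only some continue, in the GENIE and usual-care arms.

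- GENIE arm, change from baseline: p − g + s1
- Usual-care arm, change from baseline: p + s0
- Difference between arms: (p − g + s1) − (p + s0) = −g + (s1 − s0)

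Item a) does not say whether it uses the GENIE arm alone or both arms. Pooled in equal numbers, the result is p − g/2 + (s1 + s0)/2. Either way p stays in the answer.

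- With full continuation (s1 = s0 = 0) and no control exposed, the GENIE-arm result is p − g. If p = g it is zero and the benefit is invisible; if p > g it reads as worsening.
- With g = 0, the result is p + s1, which looks like improvement whenever s1 is more negative than −p.
- The arm difference removes p and any selection common to both arms. It leaves s1 − s0, the part of selection that differs by arm.

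If the comparison is paired, selection acts through those who worsened being less likely to continue. If all baseline values are set against 12-month responders, losing participants with high baseline CAT lowers the mean as well. Item a) does not say which is meant.

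**2. When the offer could fall.** Recruitment is expected to take 6 to 9 months (R) and can be extended. Assume uniform recruitment, completion at the last 3-month visit, and an analysis lag of A months (assumed; not in the documents). The offer comes at month R + 3 + A, and a participant who enters at month t is surveyed at t + 12. The share surveyed at or after the offer is 1 − (R + 3 + A − 12)/R, limited to the range 0 to 1.

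| Lag A | R = 6 | R = 9 |
|---|---|---|
| 0 | 100% | 100% |
| 3 | 100% | 1 − 3/9 = 67% |
| 6 | 1 − 3/6 = 50% | 1 − 6/9 = 33% |

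If completion instead means the last 12-month survey (month 18 to 21), the share is 0%. These are shares of surveys that follow the offer, not shares of controls who take GENIE.

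**3. What an arm comparison could detect.** The plan envisages 30 to 60 per arm. Assuming a two-sided 5% test, 80% power and no baseline adjustment, the detectable standardised difference is (1.96 + 0.84) × √(2/n): 0.72 at n = 30 and 0.51 at n = 60. For those same differences, power falls to 71% if 80% continue and 58% if 60% continue. The retention levels are assumptions.

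**The case against.** The strongest reply is that the 12-month phase is labelled potential, sits under Future work, and corresponds to no endpoint in the Objectives. Voluntary continuation is normal in consented follow-up, and the 3-month comparison is untouched. All of that stands and lowers the severity. It does not make item a) fit for its stated purpose: the phase has an aim, a visit column and an analysis, and if run as written it yields a figure that invites misreading.

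Several stronger readings are tempting but not supported:

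- *Controls will be given GENIE before the 12-month survey.* The offer depends on benefit being seen, can be declined, and follows a completion that is undefined. Future work speaks of the study's initial 3 months, which suggests an early end, but it also describes those who continue as staying in the study, which suggests a later one.
- *The 12-month contrast shrinks by a known fraction.* Shrinkage in proportion to control uptake assumes that late users gain the full benefit at once. Uptake is not given, and the present plan contains no such contrast.
- *Control use of GENIE would go unrecorded.* The data capture form and the uptake survey are not reproduced, so this cannot be judged.
- *Participants are asked to continue only after month 3.* The protocol does not say when they are asked, and the consent form is a separate document.
- *The 12-month data could show nothing about durability.* Crossover and voluntary continuation would bias or dilute an arm comparison without making it impossible. The stronger limitation applies to the before-after analysis as written.

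**Conclusion.** The point holds for the planned analysis. A comparison with own baseline cannot attribute a lasting change in CAT to GENIE, even with complete follow-up and unexposed controls. This rests on the wording of item a), on the protocol's own description of COPD as progressive, and on the absence of any between-arm analysis at 12 months. The direction of error is not fixed: progression pushes the result towards apparent harm, and selective continuation could push it towards apparent benefit. That sicker participants would be the ones to stop is plausible inference, not something the documents state. No size can be given, because p, g, s1 and s0 are all unknown.

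Control exposure is a secondary, conditional risk. On the calendar assumptions above, between none and all of the 12-month surveys could follow the offer, depending mainly on what completion means. Severity is low to moderate.

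**What to change.** 1. In the 12-month section of the Analysis Plan, replace item a) with a comparison of the randomised arms on the 1-year CAT, adjusted for baseline CAT and reported with a confidence interval. State the number continuing in each arm. Keep change from baseline as description only.
2. In Risks / benefits, state whether completion of the study falls before or after a participant's 12-month survey, and align Future work with that statement. If it falls before, record the date on which any control receives GENIE and report the 12-month result as immediate versus delayed GENIE.

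The cost is small: edits to three sections, a little more analysis and, at most, one recorded date. No new clinical measurement is needed. The arm comparison will be less precise than a within-person change and remains open to selection where continuation differs between arms, so the report should say so.
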